4.4 Data Transformation

No transformation of the data is planned other than for volume of stroke. Note that stroke volume data are often dispersed and highly non-normal and may be normalized with a cubic root transformation. No data transformation is planned for the primary analysis.

4.5 **Pooling of Sites**

In order to avoid sparse sites (sites with fewer than 10 randomized subjects) and the potential for too many levels for the explanatory variable of "site", sites within a geographic region (North America/Europe/Rest of World) with fewer than 10 randomized subjects will be pooled into a single pooled site for use in efficacy analyses. If a resulting pooled site still has fewer than 10 randomized subjects, it will be further pooled with the smallest remaining unpooled site(s) from that geographic region. If the resulting pooled site for another geographic region. The process of pooling sites will be reviewed and finalized before the unblinding of the main trial for the Day 90 analysis (i.e. first database lock as described in Section 1.3).

If more than one batch of nerinetide is used in the clinical trial, data from all subjects from all sites in the trial, regardless of the nerinetide batch administered, will be pooled for the purpose of analyses in this statistical analysis plan. Data from different batches will be pooled following the demonstration of equivalent quality of the clinical trial material based on the established release and stability testing of the nerinetide drug product batches used in the trial.

4.6 Pooling of Data from the Two Time-to-Randomization Strata

Since the randomization will be stratified by time from stroke onset to randomization \leq 4.5 hours (yes/no), the assessment for treatment-by-stratification variable interaction to examine for effect modification will be performed via a log-binomial generalized linear model as described in Section 6.1.3. In addition, homogeneity of the randomization stratification factor will be tested via Breslow-Day statistic²². If there is no evidence for effect modification, then we will report the data for the entire cohort only. If there is evidence for effect modification, the effect size for the primary, secondary and tertiary outcomes will be additionally reported by stratum.

5 DISPOSTION AND DEMOGRAPHICS

5.1 Subject Disposition

Subject disposition will be summarized and tabulated for ITT, PP and Safety populations. The summaries will include the number and percentage of subjects that completed the study and those that terminated early from the study (i.e., left the study prior to the Day 90 visit). Early terminations will be categorized by the reason for study discontinuation. Death will not be considered early termination. A tabulation of the number and percentage of subjects randomized will be summarized by site for the ITT population.

Disposition will be listed by treatment arm and subject.

5.2 **Protocol Violations**

Protocol violations used to exclude subjects from the per-protocol analysis will be derived from the data collected in the case report form. Protocol violations will be determined during a data review meeting prior to database lock. Participants will be excluded from the per-protocol analysis for the following violations:

- Enrollment did not comply with inclusion/exclusion criteria
- Subjects who did not receive a per-protocol dose including: did not receive planned dose volume, received an incorrect study drug vial, or received the study drug infusion over more than 15 minutes.
- Consent not obtained (including incorrect Deferral of Consent where applicable).

The number and percentage of subjects in the ITT population with protocol violations will be summarized by treatment group and overall. These protocol violations will be listed by treatment arm and subject.

5.3 Treatments

Per protocol, an intravenous solution of nerinetide 20mg/ml will be given to subjects with a body weight < 105 kg to achieve a final target dose of nerinetide 2.6 mg/kg. Subjects weighing 105-120 kg will each receive a total dose of 270 mg of study drug (i.e., the entire 13.5 ml contained in the study drug vial).

At the time of randomization, the dose will be calculated based on actual known weight (e.g., using an in-hospital scale) or on the subject's estimated weight. If the dosing weight was estimated, actual weight will be obtained by Day 5. Discrepancies between the weight estimate and actual weight obtained may result in some subjects not receiving the correct actual dose.

Site staff will record the total volume of nerinetide solution received by each subject and their weight at the time of dosing as well as the actual weight if an estimated weight was used. The following measures of the timeliness of the interventions and of exposure will be computed as follows.

- 1) Number and percentages of subjects who received any nerinetide
- 2) Descriptive statistics for:
- Time from stroke symptom onset to start of nerinetide infusion (minutes)

- Time from randomization to start of nerinetide infusion (minutes)
- Time from NCCT to start of nerinetide infusion (minutes)
- Duration of study drug infusion (minutes)
- Duration of study drug infusion (categorical): < 9 minutes, 9-11 minutes, > 11 minutes
- Actual administered volume of study drug (mL)
- Dosing compliance (%)
- Dosing compliance is calculated as actual administered volume of study drug divided by the baseline calculated volume of study drug * 100. The baseline calculated volume of study drug is the calculated volume based on the estimated or actual body weight at the time of randomization as recorded on the Case Report Form,
- Number and percentages of subjects compliant with study drug, a subject is considered compliant with study drug if the percent dosing compliance is ≥ 75% and ≤ 125% of planned volume.

All measures will be summarized for the ITT population; individual exposures will be listed by treatment arm and subject.

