- 4. At baseline estimated or actual weight will be collected. If an estimated weight was collected at baseline, actual weight should be collected as soon as feasible and prior to discharge.
- 5. Vital signs (BP, HR only) will be recorded immediately before and after completion of the study drug infusion, temperature will be collected at baseline only if standard of care.
- 6. Historical (pre-stroke) mRS score can be collected at any time.
- 7. MRI head may be supplanted by an NCCT head if MR is unavailable or contraindicated.
- 8. Blood should be drawn at baseline, but results are not required prior to randomization. Results from primary hospital (within 8 hours) are accepted.
- 9. If the participant is female and is of childbearing potential a pregnancy test (urine or serum point-of-care pregnancy test) must be completed and the result must be negative; this is the only mandatory laboratory test prior to randomization.
- 10. PK samples will be collected from up to 100 participants: pre-dose and at 10, 20, 30 and 60 min after the start of study drug administration.

d = days; h = hours

Contact	V7
	1-Year Follow up
Day	Day 365
Window	(±30 d)
Mortality	X
EQ-5D-5L	X
mRS	X
Barthel Index	Х

Table 1-2: Schedule of Activities: 1-Year Follow Up Telemedicine or Telephone Contact

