6.7 Treatment of Overdose

For this trial, any dose of study drug greater than 150% of the planned dose will be considered an overdose.

The sponsor does not recommend specific treatment for an overdose. In the event of an overdose, the investigator should:

- 1) Contact the Drug Safety Department ([contact]) immediately.
- 2) Closely monitor the participant for any AEs/SAEs and laboratory abnormalities for at least 1 day.
- 3) Document the quantity administered in the CRF.

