9.2 Analysis Sets

For purposes of analysis, the following populations are defined:

Population	Description
Enrolled	All participants randomized into the trial.
Randomly Assigned to Study Intervention	All participants who received a dose or partial dose of study drug

Intent to Treat (ITT)	All participants randomized into the trial with grouping by randomized treatment, regardless of treatment actually received. Participant grouped according to the randomized (intended) treatment.
Per Protocol (PP)	All participants randomized and treated, with no major protocol deviations including: did not meet inclusion/exclusion criteria, did not receive planned dose volume, incorrect study drug vial, infusion more than 15 minutes, consent not obtained.
Safety	All participants randomly assigned to study intervention and who receive any volume of study drug. Participants will be analyzed according to the intervention they actually received.

The primary efficacy estimand analysis will be conducted in the ITT population. The primary efficacy estimand analysis will be repeated on the Per Protocol (PP) population. An ITT analysis will also be conducted for the secondary endpoint estimands, with participant grouped according to the randomized (intended) treatment.

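### SAP 5.3 compliance compares the volume given with the volume planned, so it cannot show dosing error from an estimated weight, and no planned output gives mg/kg on measured weight

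*Combined protocol and SAP*

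**What the plan says.** Protocol 6.2 sets the volume below 105 kg at 2.6 mg/kg times weight divided by 20 mg/mL, and one full vial (13.5 mL, 270 mg) from 105 to 120 kg. It allows either an estimated or an actual weight to be used.

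SAP 5.3 recognises the consequence: "Discrepancies between the weight estimate and actual weight obtained may result in some subjects not receiving the correct actual dose". It has sites record the volume given and "their weight at the time of dosing as well as the actual weight if an estimated weight was used". Its compliance measure is then: "Dosing compliance is calculated as actual administered volume of study drug divided by the baseline calculated volume of study drug * 100". The reference volume is fixed at randomization: "The baseline calculated volume of study drug is the calculated volume based on the estimated or actual body weight at the time of randomization". The compliant group is defined on the same ratio: "a subject is considered compliant with study drug if the percent dosing compliance is ≥ 75% and ≤ 125% of planned volume".

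The other exposure measures in SAP 5.3 are the number receiving drug, several time intervals, infusion duration and volume in mL. SAP 5.5 summarises dosing weight and in-hospital weight as two separate demographic variables. SAP 6.5 lists concentrations and PK parameters. None of these is a dose in mg or mg/kg.

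Two neighbouring rules also refer to what was planned. The per-protocol exclusion in protocol 9.2 (also SAP 2.3 and 5.2) reads "did not receive planned dose volume". Protocol 6.7 states that "any dose of study drug greater than 150% of the planned dose will be considered an overdose". Neither says which weight defines the plan.

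**The concern.** The treatment is defined per kilogram, so dose accuracy has two parts: whether the calculated volume was infused, and whether it was calculated from the right weight. SAP 5.3 names the second part as a source of error, has the data for it collected, and then measures only the first. A reader of the exposure table could take a high compliance percentage as evidence that participants received close to 2.6 mg/kg, which the ratio cannot show.

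Two planned uses would benefit from a received dose. Protocol 9.3.4 intends to examine dose proportionality, yet every participant has the same nominal regimen and neither document derives a received dose to serve as the explanatory variable. Hypotension is a named risk (protocol 2.3.1) and an event of special interest (protocol 8.3). The previous Phase 3 trial had 6 serious cases on nerinetide and 0 on placebo soon after dosing (protocol 2.1.5). No planned table sets these events beside the mg/kg received.

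**Working it through.** **Inputs.** Concentration 20 mg/mL, dose 2.6 mg/kg, and vial volume 13.5 mL are from protocol 6.1 and 6.2. The compliance formula and the 75-125% band are from SAP 5.3. The size of the weight error is not in the documents and is assumed.

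**Plan's own figure.** 13.5 mL × 20 mg/mL = 270 mg, which reproduces.

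**Formulas (below the cap).**
- Planned volume = 2.6 × dosing weight / 20.
- SAP compliance = volume given / planned volume × 100.
- Dose received = volume given × 20 / measured weight.

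If the full planned volume is given, compliance = 100 whatever the measured weight, and dose received = 2.6 × dosing weight / measured weight. The measured weight does not enter the compliance formula.

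**One case.** Dosing weight 80 kg: 2.6 × 80 / 20 = 10.4 mL, and 10.4 × 20 = 208 mg. If the measured weight is 100 kg, the dose is 208 / 100 = 2.08 mg/kg, which is 80% of 2.6. Compliance is 10.4 / 10.4 = 100%.

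**Assumed range, full planned volume given.**

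| Measured weight relative to estimate | Dose received (mg/kg) | Percent of 2.6 | SAP compliance |
|---|---|---|---|
| +20% | 2.6 / 1.2 = 2.17 | 83% | 100% |
| +10% | 2.6 / 1.1 = 2.36 | 91% | 100% |
| -10% | 2.6 / 0.9 = 2.89 | 111% | 100% |
| -20% | 2.6 / 0.8 = 3.25 | 125% | 100% |

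If the error is instead expressed as a percentage of the measured weight, the ranges are 2.34-2.86 mg/kg (±10%) and 2.08-3.12 mg/kg (±20%).

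**When the band itself would be crossed.** With full volume given, the percentage on measured weight is 100 × dosing weight / measured weight. It leaves 75-125% only if measured weight is below 1 / 1.25 = 0.80 or above 1 / 0.75 = 1.33 times the estimate. Errors of up to ±20% therefore change the mg/kg distribution but, alone, do not move anyone out of the band.

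**Where the effect shrinks.** If estimated and measured weight both lie between 105 and 120 kg, the dose is 270 mg either way and there is no error. Near that range, overdosing is limited by the vial: an estimate of 110 kg with a measured 100 kg gives 270 / 100 = 2.70 mg/kg, or 103.8% of 2.6.

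**The case against.** The strongest reply is that the formula is right for what it measures. Because the protocol permits an estimated weight, the volume calculated from it is the planned dose, and compliance properly asks whether that volume was given. This stands: the ratio should be kept, and what is missing is a second measure.

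It is also fair that the protocol already accepts doses below 2.6 mg/kg: the cap gives 270 / 120 = 2.25 mg/kg at 120 kg. Moderate departures are thus not alien to the design. They are, however, known from the weight, whereas those from estimation error are not tabulated anywhere.

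Several stronger readings are tempting but unsupported:
- *The measured weights go unused.* SAP 5.5 summarises them; they are only not combined with volume.
- *A hypotension event could not be linked to the dose received.* SAP 5.3, 5.5 and 7.1 list exposures, demographics and events of special interest by subject, so the value is one division away.
- *Compliance would look near-perfect whatever was received.* A stopped infusion or a preparation error lowers the ratio. Only weight-estimation error is invisible to it.
- *A null result could not be told from underdosing.* That would need systematic underestimation of weight, which the two weight summaries could reveal. The trial is randomised and blinded, and nothing in the documents suggests that errors differ by arm.
- *A dose above 150% on measured weight escapes the overdose rule.* Protocol 6.7 does not say which weight defines the planned dose, so this is only one reading. The per-protocol dose criteria in SAP 5.2 are likewise not clearly exhaustive, and deviations are settled in a review before lock.

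**Conclusion.** The point holds as a gap in exposure reporting. The SAP's only dose-accuracy measure does not respond to the dosing error that SAP 5.3 itself anticipates, and no planned output gives mg or mg/kg on measured weight, although every input is recorded. The primary ITT analysis is unaffected.

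The size depends on two unknowns: how many participants are dosed on an estimate, and how far the estimates are off. Under assumed errors of ±10% and ±20% of the estimated weight, with full volume infused and the cap not reached, doses of 2.36-2.89 and 2.17-3.25 mg/kg would all be reported as 100%. This is an inexpensive improvement and not a threat to the trial's main conclusion.

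**What to change.** In SAP 5.3:
1. Derive actual dose (mg) = administered mL × 20 mg/mL, expressed as the volume equivalent for placebo.
2. Derive actual mg/kg = that dose / measured weight, and the percentage of the protocol-specified dose for the measured weight, taking the 270 mg maximum into account.
3. Summarise these by arm, with the number and percentage inside and outside the existing 75-125% band.
4. Show participants without a measured weight as a separate category. Substituting the dosing weight would return them to 100%.
5. Keep the present ratio, labelled as volume given versus volume planned.
6. Use the derived dose in the dose-proportionality work of protocol 9.3.4, and print it beside the hypotension entries in the listing of events of special interest.

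A reader might also want the primary endpoint re-analysed in participants inside the band on measured weight. This is not needed: it selects on post-randomisation data and on whether a weight was obtained. If it is done, it should be labelled exploratory.

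The sponsor should also reconcile three texts:
- which weight defines the planned dose in protocol 6.7;
- when the actual weight is due, since SAP 5.3 says by Day 5 while protocol Table 1-1, note 4 says "If an estimated weight was collected at baseline, actual weight should be collected as soon as feasible and prior to discharge";
- the volume formula just under 105 kg, which exceeds one vial above 270 / 2.6 = 103.85 kg (at 104.9 kg, 2.6 × 104.9 / 20 = 13.64 mL).

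The cost is a few lines of SAP text and a short set of derived variables. Volume, dosing weight and later actual weight are already recorded, so no new data are needed.

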5.4 Study Progress Time

The following study progress time parameters will be summarized by treatment group and overall on ITT Population.

- Time from Stroke Onset to study drug infusion start (minutes)
- Time from ESCAPE-NEXT hospital arrival to study drug infusion start (minutes)
- Time from to study drug infusion start to initial reperfusion* (minutes)
- Time from ESCAPE-NEXT hospital admission to hospital discharge (days)
- Time in repatriation hospital (days)
- Time in inpatient rehabilitation (days)

*time of initial reperfusion is defined as the time logged for the first mTICI score.

5.5 Demographic and Baseline Characteristics

Subject demographic and baseline characteristics will be summarized with descriptive statistics for each treatment group. Demographic variables include, but are not limited to: age, sex, race-ethnicity, weight at time of dosing (in kg), and weight as determined in hospital (in kg). Baseline characteristics include but are not limited to: age, sex, baseline NIHSS score, baseline ASPECT score, occlusion location, time from stroke symptom onset to randomization (hours), time from stroke symptom onset to randomization ≤ 4.5 hours (yes/no), time from qualifying imaging to randomization, unwitnessed stroke onset (yes/no), stroke-on-awakening (yes/no), and site. The summaries will be provided for the ITT, Per Protocol and Safety populations. Inferential statistics (i.e., p-values or CI) will not be provided for the stratification variable "Time from Stroke Onset to Randomization ≤ 4.5 hours" (yes/no)" in order to assess balance across treatment groups. Demographics will be listed by treatment arm and subject.

Relevant past medical history as well as prior and concomitant medications will be summarized and listed.

6 EFFICACY ANALYSIS

Two separate efficacy analyses are planned for this trial. The first analysis will be based on the completion of Day 90 visits for the main trial as described in Sections 6.1 to 6.5 below. The second analysis will be following the completion of the 1-Year follow up for the analytic sub-trial as described in Section 6.6 below.

A priori, we will assess for treatment-by-stratification variable interaction to examine for effect modification (details below). If there is no evidence for effect modification, then we will report the entire cohort only. If there is evidence for effect modification, we will additionally report results by stratum.

Efficacy analyses are summarized in Table 4: Summary of Inferential Efficacy Analyses.

6.1 Primary Outcome Variable Analysis for Main Study

6.1.1 Primary Estimand

The primary estimand is defined as the difference in the mRS response (i.e. mRS score of 0-2) proportions between treatment conditions (nerinetide vs. placebo) in the target patient population at Day 90. Death occurring prior to Day 90 will be considered as non-response.

6.1.2 Statistical Hypothesis

The primary hypothesis is:

H₀: $\pi_{\text{nerinetide}} = \pi_{\text{placebo}}$ VS H_a: $\pi_{\text{nerinetide}} \neq \pi_{\text{placebo}}$

Where $\pi_{nerinetide}$ and $\pi_{placebo}$ are the nerinetide and placebo population proportions of responders, defined as subjects whose Day 90 mRS score is ≤ 2 .

6.1.3 Primary Efficacy Estimand Analysis

Primary statistical analysis for primary estimand

The primary analysis for the primary estimand will be conducted in the ITT population according to the randomized treatment. Missing data will be imputed following the single imputation approach in Section 4.3.2.

The primary hypothesis to be tested is that administration of nerinetide will result in an increase in the proportion of mRS responders (as defined by a score of 0-2) at Day 90.

The pivotal primary analysis will be conducted on the ITT population at the 2-sided 0.05 significance level overall (for the trial), adjusted for the interim analysis per the O'Brien-Fleming boundary spending function.

The pivotal main effects primary analysis will use a multivariable generalized linear model (GLM) using a binomial distribution with a log link to provide adjusted relative risk (log-binomial regression). Adjustment will include the stratification covariate of time from stroke onset to randomization \leq 4.5 hours (yes/no) and the randomized minimization (age, sex, baseline NIHSS score, baseline ASPECT score, occlusion location, time from qualifying imaging to randomization and pooled site).

The main effects primary analysis will be supported by a further analysis in which the GLM used for the pivotal analysis also includes the interaction term (treatment by randomization stratification factor). If the interaction term is significant at the 0.05 level, we will additionally

Version: 2.0	SAP NA-1-009
Date: 18 November 2021	NoNO Inc

repeat the primary analysis, sensitivity analyses, the supportive analyses described below, and the analyses for the secondary efficacy estimand analyses and tertiary efficacy outcome analyses for each stratum separately. If the interaction term is not significant at the 0.05 level, the data for each stratum will not be reported separately.

If a binomial distribution model fails to converge, accepted methods using multivariable logistic or Poisson regression with robust error variance will be used to provide adjusted relative risk.

Example SAS code for the log-binomial regression model as follows:

```
PROC GENMOD DATA = ADMRS;
CLASS TRTPN RANDTIME SEX BASPECT OCCLOC SITEGR1;
MODEL CRIT1FN(event="1") = TRTPN RANDTIME AGE SEX BNIHSS
BASPECT OCCLOC IMA_TIME SITEGR1 / DIST = BINOMIAL LINK=LOG;
ESTIMATE "NA-1 vs. placebo" TRTPN 1 -1 / exp;
```

RUN;

Example SAS code for the Poisson regression model:

```
PROC GENMOD DATA = ADMRS;
CLASS TRTPN RANDTIME SEX BASPECT OCCLOC SITEGR1 USUBJID;
MODEL CRIT1FN = TRTPN RANDTIME AGE SEX BNIHSS BASPECT
OCCLOC IMA_TIME SITEGR1 / DIST = POISSON LINK=LOG;
REPEAT SUBJECT=USUBJID / TYPE=IND;
ESTIMATE "NA-1 vs. Placebo" TRTPN 1 -1 / exp;
```

RUN;

Where CRIT1FN is a numeric variable to indicate binary mRS responder status (1 = responder, 0 = non-responder), TRTPN is a numeric variable for treatment group (1 = nerinetide group, 2 = placebo), USUBJID is the subject ID.

The conditional treatment effect (i.e. relative risk) along with the 95% CI, as well as the corresponding Wald test statistics and p-value estimated from the above model will be reported. Actual proportions with and without independent functioning (i.e. mRS responders and non-responders) will be reported.

In addition, the unconditional treatment effect will be estimated and reported following below steps:

- 1. Run the primary analysis model (adjusted log-binomial regression) as described above.
- 2. For each subject, compute the model-based prediction of the probability of mRS response under nerinetide in both the nerinetide group and placebo group using each subject's specific baseline covariates (i.e. as specified in the primary analysis model)
- 3. Estimate the average response under nerinetide by averaging (across all subjects in the ITT population) the probabilities estimated in Step 2
- 4. For each subject, compute the model-based prediction of the probability of mRS response under placebo in both the nerinetide group and placebo group using each subject's specific baseline covariates

- 5. Estimate the average response under placebo by averaging (across all subjects in the ITT population) the probabilities estimated in Step 4
- 6. The estimates of average mRS responses rates in the two treatment groups from Steps 3 and 5 will be used to estimate the relative risk (i.e. unconditional treatment effect)

The 95% CI of the unconditional treatment effect will be constructed using a nonparametric bootstrap resampling, with 1000 resamples and subject as the unit of resampling. Resampling will be done independently for the nerinetide and placebo subjects. For each resample, Steps 1-6 will be repeated. The 95% CI of the unconditional treatment effect will then be determined from the distribution of resample relative risks.

Sensitivity analyses for the primary estimand

Sensitivity analyses in the ITT population will be conducted in which missing values are not imputed, i.e. observed cases (OC). In addition, the following analyses will be also be performed depending on the amount of missingness observed:

- If \leq 5% of participants randomized are missing the Day 90 mRS assessment, a sensitivity analysis will be performed for the primary estimand by using only participants having completed Day 90 mRS assessments. Participants who are known to be dead before or at Day 90 will also be included as non-responders.
- If more than 5% participants randomized are missing the Day 90 mRS assessment:
 - a sensitivity analysis will be performed for the primary estimand with missing data imputed by MI (refer to Section 4.3.2)
 - A tipping point analysis will be performed to assess the robustness of the MAR assumption about the missing primary outcome

The sensitivity analysis performed on multiple imputed datasets will follow these steps:

- 1. For each of the multiple imputed datasets, the primary analysis model, i.e. adjusted logbinomial regression, will be performed. The log (relative risk) and the standard errors will be obtained.
- 2. The point estimate of the log (relative risk) and standard errors obtained from Step 1 will be passed to PROC MIANALYZE to generate a combined result. The combined log (relative risk), relative risk and associated 95% CI and the resulting p-value will be reported.

Supportive analyses for the primary estimand

Additional supportive analyses will be conducted in addition to the primary and sensitivity analysis to provide additional insights into the understanding of the treatment effect.

The primary analysis will be supported by a Cochran-Mantel-Haenszel test to evaluate the association between treatment and the primary outcome stratified by the randomization stratification variable (time from stroke onset to randomization \leq 4.5 hours (yes/no). Homogeneity of the randomization stratification variable will be tested via Breslow-Day statistics. The common relative risk (nerinetide/placebo) over all strata with its 95% CI and p-value will be reported.

Example SAS code for the Cochran-Mantel-Haenszel test is as follows:

PROC FREQ DATA = ADMRS;

TABLES RANDTIME*TRTP*CRIT1FL / CMH;

RUN;

A further supportive analysis will be an unadjusted two-sample comparison of binomial proportions via Wald test from logistic regression stratified on the randomization stratification factor (time from stroke onset to randomization ≤ 4.5 hours (yes/no)) to match the randomization. Estimated proportions (% responders) will be reported with binomial confidence intervals.

Example SAS code for the logistic regression test is as follows:

```
PROC LOGISTIC DATA = ADMRS;
CLASS TRTP (PARAM=REF REF='Placebo');
STRATA RANDTIME;
MODEL CRIT1FL(EVENT="Y") = TRTP;
ODDSRATIO TRTP / CL=WALD DIFF=ALL;
```

RUN;

Where CRIT1FL is the binary mRS responder status (yes/no).

Two additionally supportive analyses to the primary analysis will be conducted: (1) the primary analysis reapplied to the Per Protocol population with observed cases (OC) only; (2) a re-randomization analysis to demonstrate that minimization did not bias the primary endpoint analysis. The later test will consist of rerunning the randomization 5,000 times on the original subjects' data and then performing the primary endpoint analysis on each of the re-randomized data sets. This will yield a distribution of 5,000 p-values that will correspond to the p-value distribution expected under the null hypothesis of no nerinetide effect. The p-value from the actual primary analysis will be compared to the distribution of randomization p-values. If (for example) the minimization was unbiased and actual p-value was 0.01, we would expect P=0.01 to be near the 1st percentile of the distribution of the 5000 p-values. A variant of this methodology was successfully used to validate the minimization in the ESCAPE² and ESCAPE-NA1⁴ trials.

Baseline, Day 6/Discharge, Day 30 and Day 90 mRS scores will be listed by treatment arm and subject.

